Reason Not Completed Type. The reasons for not completing the study included only the following, and were fully recorded: Metal thread behind front teeth (1); Excluded by project staff due to frivolous attitude towards the study (1); Physiological hindrance of drawing blood from subject (1); Blood sampling not possible (2); Personal issues without the possibility of rescheduling (1)

2. Baseline Characteristics

Arm/Group Information. Baseline characteristics will be computed in the form of standard summary statistics (means, standard deviations, Bayesian credibility intervals) $\textbf{Baseline Measure Information.} \ \textbf{A} \ \text{group of demographic characteristics will be measured in}$ the study, including: age; gender; weight; height; educational level; income;

Baseline Measure Title. Age: Continuous (years); Gender: Categorical (female, male); Weight: Continuous (kg); Height Continuous (meter); Educational level: Categorical (lower secondary, higher secondary, higher secondary with trainee, short-length higher education, mediumlength higher education, long-length higher education); Income: Categorical (< 100.000 Dkkr, 100.000-199.999 Dkkr, 200.000-299.999 Dkkr, 300.000-399.999 Dkkr, 400.000-599.999 Dkkr, 600.000-799.999 Dkkr, ≥ 800.000 Dkkr, do not wish to inform)

Measure of Dispersion. Standard Deviation, Interquartile ranges, Range

3. Outcome Measures

 $\label{lem:composition} \textbf{Outcome Measure Information.} \ \text{The primary outcome is the energy consumed in the ad}$ libitum meal.

Outcome Measure Type. Primary Outcome Measure Title. Energy consumed

Outcome Measure unit. kJ

Outcome Measure Time Frame. There will be four such measurements per participant, one for each condition. These are taken at the end of the experimental testing day Overall Number of Participants Analyzed. There will be data analysed from 23 participants.

Measure Type. Means Measure of Dispersion/Precision. Standard Deviation and Bayesian central credibility intervals Outcome Data. The measurement value(s) for each outcome measure cannot obtain right now since data collection has not finished yet.

Comparison Group Selection. There is only 1 group.

Statistical Testing.

Statistical modelling of multimodal metric

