The aim of neuroimaging analysis is to delineate the interoceptive neural systems underpinning satiety, and its interface with behavioral and endocrine systems. Broadly we hypothesise that tonic & food cue-evoked activity in viscerosensory & visceromotor networks, will be predictive of next-meal energy intake, specifically in Hypothalamus & Insula and more broadly in regions of interest: ACC, OFC, SGC, PBN, NTS, amygdala, striatum. We will engage in exploratory data analysis by mapping the neural modulations caused by post-prandial endocrine dynamics. Finally we will extract key features of data from regions of interest to assess how neural activity can predict energy intake. For the functional neuroimaging data, a multiple linear regression model will be constructed via the software Statistical Parametric Mapping. The onset of food and object images will be modelled as stimulus onsets using $standard\ methods,\ convolving\ stick\ functions\ representing\ stimulus\ onsets\ with\ hemodynamic$ response functions. Regressors of interest will include food images classified according to high or low energy density, and objects. Resting state data will be modelled according to standardized pipelines. We will compute the main effect of caloric density of food cues. We will compute the Parametric modulations of blood and subjective covariates on these caloric density responses. We will compute the main effect of endocrine and subjective covariates as slow varying modulators of resting activity. Multivariate Bayesian decoding will be performed on regions of interest to ask which brain regions decode onto endocrine responses, subjective responses, and ultimately energy intake.

Statistical modelling of endocrine responses

In modelling the endocrine responses we will focus on 2 physiological modalities; appetite sensation (outcome=energy intake) and nutrient sensing (outcome=hormone responses). 1. Appetite sensation: To address the question of how well endocrine responses predict energy intake we will perform a linear regression models with energy intake as dependent variable and AUC of endocrine metabolic marker and energy expenditure (calculated from height and weight) as covariates (and subject id as random effect). A regression model will be performed for each of the different endocrine markers to find the marker that explains the maximum variance in energy intake.

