In addition, we will perform a Bayesian linear regression (as described in preceding section), with energy intake as dependent variable. The regressors of interest will be based on area under the curve metrics computed from all of the endocrine and metabolic markers obtained from the blood sampling including GLP1, Ghrelin, PYY, CCK, glucose, insulin.

2. Nutrient sensing: To address the question of between preload effects on endocrine responses we will perform a repeated measures 2-way ANOVA with AUC of endocrine marker as dependent variable and both preload dimensions as independent fixed effects and individual subject id as an independent random effect. Post hoc pairwise multiple-comparisons will be used as follow-up tests to compare every group mean.

4. Adverse Event Information

Time Frame. Possible adverse events can include fainting at the point of drawing blood. This is monitored by two researchers at all times, where the participant is vulnerable to fainting. Adverse Event Reporting Description. We will add relevant information about adverse event after finishing the study

5. Limitations and Caveats

There may be several limitations or caveats. First, it is possible that the dietary intervention does not impact on energy consumption hours later. The dietary intervention is primarily used as a manipulation to drive variation in consumption. As long as consumption has variance across and within participants, then the main goal of using the data modalities to predict satiety is still achievable. Second, it is possible participants do not comply with instructions prior to their experimental day. This will be evident in the blood measures, indicating for instance if they have not fasted. Non-compliance could be evident in their tracker activity, for instance if they have engaged in extreme activity prior to testing. However not all such cases can be inferred from these measures.

6. Certain Agreements

Are all Pls Employees of Sponsor? No. There is one sponsor-investigator and none of the other principal investigators are employed by the sponsor.

Results Point of Contact

Name. [name] [name], PhD Position title: Post Doc

Organization Name. University of Aarhus

[contact]

Email. [contact]

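### One leading hormone marker is named from separate regressions with no uncertainty on the ranking; if the top markers are close, the wrong one is named in roughly 20–55% of trials

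*Combined protocol and SAP*

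**What the plan says.** In section 3 (Outcome Measures), under the modelling of endocrine responses, item 1 (Appetite sensation) asks how strongly hormone responses predict energy intake. It models intake on a marker's area under the curve, with energy expenditure as a covariate and subject as a random effect. It then says: "A regression model will be performed for each of the different endocrine markers" and gives the purpose as "to find the marker that explains the maximum variance in energy intake".

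The candidates are listed in the next paragraph as "including GLP1, Ghrelin, PYY, CCK, glucose, insulin". That is six named markers, and the wording leaves room for more. On the amount of data, section 3 says "There will be data analysed from 23 participants" and, on energy intake, "There will be four such measurements per participant, one for each condition".

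The same next paragraph adds a joint analysis of all the markers: "In addition, we will perform a Bayesian linear regression (as described in preceding section), with energy intake as dependent variable". The multimodal-metric part of section 3 describes a Bayesian regression that yields inclusion probabilities and Bayes factors for each regressor.

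No interval for variance explained, comparison between markers, resampling, or condition for naming a marker is attached to the separate regressions. The type of R-squared for a model with a random effect is not defined. Section 5 (Limitations and Caveats) does not mention the point.

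**The concern.** Taking the maximum of six or more estimated R-squared values always returns a name. If the markers are equally good, the name is arbitrary. If they are close, it depends heavily on which 23 people took part. A reader who is told which marker came first cannot tell these situations from one in which a single hormone really stands out.

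This is a different matter from the winning R-squared being too large. Correcting that optimism shrinks the figure but says nothing about whether the right marker is in first place. What is at stake is that an arbitrary or wrong hormone is reported as the leading endocrine predictor of intake.

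**Working it through.** The plan states no effect size, correlation or power for this analysis, so there is no figure of its own to reproduce. The rule was simulated instead.

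**Inputs from the plan.** 23 participants; 4 measurements each, so 23 × 4 = 92 meals in 23 clusters; six named markers; one model per marker; the largest R-squared wins.

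**Inputs assumed.** Correlations of markers with intake, correlations between markers, and between-person variance. None of these is in the documents, so ranges are shown.

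**Step 1: equal markers.** A winner is still named, and chance gives each marker 1/6 = 0.167. With all six at a true R-squared of 0.05, a given marker was named in 0.171–0.174 of runs. With all six correlated 0.30 with intake, the winner's median R-squared lead over second place was 0.033 and 0.024 (between-marker correlation 0.3 and 0.6).

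**Step 2: person-centred data.** With subject means removed, a marker's R-squared is its squared within-person correlation with intake, and wrong = 1 − right. The paired figures are for between-marker correlation 0.3 and 0.6.

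| Assumed correlations with intake | R-squared gap, first to next | Right | Wrong |
|---|---|---|---|
| 0.35; five at 0.25 | 0.1225 − 0.0625 = 0.06 | 47%, 57% | 53%, 43% |
| 0.40; 0.30, 0.25, 0.25, 0.20, 0.20 | 0.16 − 0.09 = 0.07 | 65%, 76% | 35%, 24% |
| 0.50; 0.40, 0.35, 0.30, 0.30, 0.25 | 0.25 − 0.16 = 0.09 | 71%, 81% | 29%, 19% |
| 0.50; five at 0.25 | 0.25 − 0.0625 = 0.19 | 92%, 98% | 8%, 2% |
| 0.50; five at 0.20 | 0.25 − 0.04 = 0.21 | 95%, 99% | 5%, 1% |

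The first three rows use 20,000 runs and the last two 1,500. Repeat runs agreed to within about 1 point. The close profiles give 19–53% wrong and the clear-leader profiles 1–8% (up to 9% in repeat runs).

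**Step 3: closer to the planned model.** Intake was regressed on marker, energy expenditure and a random subject intercept, fitted by maximum likelihood and ranked by marginal R-squared. There were 600 runs per cell, with a Monte Carlo standard error of at most √(0.5 × 0.5 / 600) = 0.02. Between-marker correlation was 0 or 0.3. The middle column is a person-centred run on the same profiles (5,000 runs, between-marker correlation 0 to 0.5).

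| True within-person R-squared, best v others | Wrong, person-centred | Wrong, random intercept |
|---|---|---|
| 0.10 v 0.05 | 51–60% | 63% |
| 0.10, 0.08, 0.06, 0.04, 0.02, 0 | 54–59% | 60–61% |
| 0.20 v 0.10 | 33–47% | 51–52% |
| 0.15 v 0.05 | 24–40% | 45–47% |
| 0.25 v 0.05 | 2–11% | 16–21% |

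In the random-intercept set-up, markers also vary between people in a way unrelated to intake. That is a likely reason why its rates are higher.

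**Step 4: would cross-validated ranking help?** Share right, in-sample v leave-one-participant-out, for the three close profiles (2,000 runs): 0.477 v 0.474 and 0.584 v 0.576; 0.651 v 0.650 and 0.754 v 0.746; 0.708 v 0.709 and 0.804 v 0.805. The largest difference is 0.584 − 0.576 = 0.008. What is missing is an uncertainty statement on the order, not a different ranking criterion.

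**Step 5: what a participant bootstrap would show** (person-centred, 1,000 runs × 400 resamples). With a true R-squared gap of 0.02–0.10, the named marker ranks first in 54–62% of resamples on average. The 95% interval for first minus second includes zero in 94.8–98.5% of trials. With a gap of 0.20 (0.25 v 0.05), the figures are 76–81% and 72–82%.

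**The case against.** **The joint Bayesian regression already gives evidence on each marker.** This stands in part and should be credited: it would be wrong to infer that the plan has no marker-level measure of evidence. But an inclusion probability measures a marker's contribution given the others. The plan does not link it to the marker named from the separate models or say what happens if the two disagree. The cross-reference to a preceding section is also loose, so it is an inference that inclusion probabilities will be reported here.

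**The marker's identity is not the main conclusion.** This stands. The question posed is predictive strength, the best marker is a subordinate aim, and no later decision in the documents depends on it. That limits the weight of the point but does not remove it, because a named marker will be read as a finding.

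**The high error rates come from near-ties.** This also stands. A reader might infer that this trial will probably name the wrong marker. The documents do not support that, because they give no correlations and a clear leader is usually found. In the near-ties, choosing the wrong marker costs only about 0.02–0.03 of true R-squared on average. That is small for prediction, but it does not help a reader who takes the name as a biological lead.

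**Ranking on point estimates alone is inferred from silence.** True, but the written rule is simply the maximum, and nothing accompanies it.

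**Conclusion.** The point holds in conditional form. Followed as written, the rule names a marker every time and gives no measure of how secure that name is. If the leading correlations are about 0.10 apart, the name is wrong in roughly 20–55% of trials on person-centred data. With a clear leader (0.50 v 0.20–0.25) it is wrong in under 10%. In the random-intercept form the range is 16–63%, and even its clear-leader scenario (R-squared 0.25 v 0.05) is wrong in 16–21%.

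All of this assumes six markers, 23 × 4 complete data, and correlations and variances that the plan does not state. None of the percentages is this trial's error rate. They show that the data could plausibly fail to separate the markers, and that the planned output would not reveal it. This is a secondary analysis, and the point does not touch the multimodal model of the primary outcome.

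**What to change.** Add to item 1 (Appetite sensation) of the endocrine modelling text:

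- State which R-squared is used for the random-effect model, and list all markers that will be ranked.
- Resample participants with replacement, keeping each person's four days together and giving repeated draws separate subject labels. Refit every marker's planned model in each resample.
- Report how often each marker ranks first, and an interval for the R-squared difference between the markers placed first and second in the actual data. Keep that pair fixed across resamples so that the difference can be negative.
- Show these beside the inclusion probabilities from the joint Bayesian regression.
- If the interval does not exclude zero, describe the top marker as leading but not separated from the others, and as exploratory.

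No fixed cut-off on first-rank frequency is needed. A rule of naming a marker only at 95% of resamples named one in just 3–17% of close cases and withheld a name in 32–73% of clear-leader cases. Reporting the smallest set that holds 90% of first places kept the true best marker in as few as 82%.

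The cost is a short script and a few sentences, with no new data. The downside is that the report will usually say that close markers cannot be separated. On the step 5 figures it will often say so at this sample size even for a true R-squared gap of 0.20.

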Official Title of the study: The Omnibus Satiety Metric (OmniSaM)

Date of the document: 1 March 2019

Full study protocol and statistical analysis plan

Contents

- 1. Participant Flow
- 2. Baseline Characteristics
- 3 Outcome Measures
- 4. Adverse Event Information
- 5. Limitations and Caveats
- 6. Certain Agreements
- 7. Results Point of Contact

1. Participant Flow

Recruitment Details. Participants were recruited via convenience sample via the website www.forsøgsperson.dk . The recruitment started oct 2017 and lasted around approx.

Pre-assignment Details. Via a phone meeting we first assess if the volunteers fulfill the inclusion-exclusion criteria. Those who meet the initial criteria for inclusion will participate in an information meeting where information about procedures will be delivered and participants can ask questions. Those who agree to participate in the study will give written consent, deliver a blood sample to be analyze for: hemoglobin, liver and kidney function and inflammatory state, and weight, height and blood pressure will be measured, to ensure the recruited people meet all the inclusion and exclusion criteria. These criteria are listed in the main clinical trials document.

Enrollment (total, anticipatory). Total whom started the study 28; Anticipated completion of all four test days 25; Fully completion of all four test days 23; Excluded from analyses 5 Allocation (randomized). This is a single arm study in which all conditions of a 2x2 factorial design and allocated to the same group in a randomized order.

Follow-up (immediately after intervention). There is no follow up.

Arm/Group Information. There is 1 arm in the study.

Arm/Group Description. All participants in this single arm study undergo a dietary intervention, comprising the 2x2 factorial design in which they are tested under four conditions in which only the dietary preload changes.

- 1. high protein2carb high calorie
- 2. high protein2carb low calorie
- 3. low protein2carb high calorie
- 4. low protein2carb low calorie

Period(s). There is only one stage in the study, comprising the four test days, one for each of the experimental conditions

Period Title. Overall Study. **Started.** 28 started the study. **Completed.** 23 finished the study.

Milestone Title. There are no follow ups so therefore no milestones.

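### The nutrient-sensing ANOVA leaves AUC undefined and omits the same-day fasting value, so day-to-day baseline variation is handled poorly; this costs precision and does not cause bias

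*Combined protocol and SAP*

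**What the plan says.** Section 3, Statistical modelling of endocrine responses, item 2 (Nutrient sensing), sets out a "repeated measures 2-way ANOVA with AUC of endocrine marker as dependent variable". Its other terms are "both preload dimensions as independent fixed effects and individual subject id as an independent random effect", followed by post hoc pairwise comparisons. No further covariate is named.

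AUC is not defined. The Bayesian regression in the same section uses "area under the curve metrics computed from all of the endocrine and metabolic markers obtained from the blood sampling" and names GLP1, ghrelin, PYY, CCK, glucose and insulin. It gives no sampling times, no baseline sample and no choice between total and incremental area.

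Section 5 (Limitations and Caveats) discusses participants who do not follow instructions before the test day: "This will be evident in the blood measures, indicating for instance if they have not fasted". It then concedes that not every such case can be detected.

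On design, section 1 says that participants undergo "all conditions of a 2x2 factorial design and allocated to the same group in a randomized order", with one test day per condition. Section 3 states: "There will be data analysed from 23 participants".

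**The concern.** A hormone AUC depends partly on where the marker stood before the preload. That starting level differs between people and also, within a person, between test days. The random subject effect deals with the first source only. The second falls into the error against which the preload contrasts and the post hoc comparisons are judged.

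A value measured before the preload cannot be altered by that day's preload, so it is a safe covariate. With 23 people analysed, avoidable noise widens every interval in this analysis. The plan appears to have the value available but gives it no role in the model.

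**Working it through.** **Is there a pre-preload sample?** The only blood sample that the documents place in time is the screening sample in section 1, and it is for other analytes. Two things point to a test-day sample before the preload. Section 5 expects blood to show failure to fast, which a sample taken only after the preload could hardly do. An AUC also needs a starting value. This is a sound inference but not a stated fact.

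**Inputs.** From the documents: n = 23, four test days each, a 2x2 within-subject design, and the model terms above. The documents give no SD, correlation, alpha, power or target effect for this analysis, so there is no planned figure to reproduce. Assumed: two-sided alpha 0.05, 80% power as the reference point, and the two quantities below.

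- *r*: within-person, day-to-day correlation of the fasting value with **total** AUC, from 0 to 0.7.
- *k*: day-to-day SD of the subtracted baseline divided by that of total AUC, shown at 0.5 and 1.

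**Residual variance**, relative to unadjusted total AUC:

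- total AUC, no covariate: 1
- same-day fasting value as covariate: 1 − r²
- incremental AUC by simple baseline subtraction, no covariate: 1 + k² − 2rk

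| r | covariate | interval narrower than total AUC, 1 − √(1 − r²) | incremental, k = 0.5 | incremental, k = 1 |
|---|---|---|---|---|
| 0 | 1.00 | 0% | 1.25 | 2.00 |
| 0.3 | 0.91 | 5% | 0.95 | 1.40 |
| 0.5 | 0.75 | 13% | 0.75 | 1.00 |
| 0.7 | 0.51 | 29% | 0.55 | 0.60 |

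The incremental variance exceeds the covariate variance by (1 + k² − 2rk) − (1 − r²) = (k − r)², which is never negative. Subtraction is worse than doing nothing whenever k > 2r. It equals the covariate only at k = r.

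**Degrees of freedom.** 3 × 23 = 69 within subjects. Removing two main effects and the interaction leaves 66, or 65 with the daily-deviation covariate.

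**Power for one main effect.** A noncentral F test with noncentrality 23d²/s², where s² is the relative residual variance and d is in within-person residual SDs of total AUC. Unadjusted total AUC detects d = 0.593 with 80% power. At that d:

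| r | total | covariate | incremental, k = 1 |
|---|---|---|---|
| 0 | 80% | 80% | 50.8% |
| 0.3 | 80% | 83.6% | 65.8% |
| 0.5 | 80% | 89.9% | 80.0% |
| 0.7 | 80% | 97.5% | 95.1% |

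With the covariate, the effect detectable at 80% power is 0.593, 0.566, 0.514 and 0.423 at the four values of r.

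**Check for bias.** In simulation (2,000 runs per setting, r = 0.3, 0.5 and 0.7), type I error lay between 4.1% and 6.1% across all three analyses. The simulation standard error is √(0.05 × 0.95 / 2000), about 0.5 percentage points. Nothing here suggests that the unadjusted analysis is invalid.

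**The case against.** The strongest reply is that the ANOVA as written is already valid. Order is randomised, the subject effect removes stable baseline differences, and the gain depends on correlations that nobody has stated and that may differ across six markers. All of that stands. Four stronger readings are tempting, and the documents do not support them.

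- **That the fasting value is certainly ignored.** AUC is undefined. If it is incremental, the fasting value is already in the outcome. The fix survives this, because the covariate variance is never above the subtracted one, but the 9% / 25% / 49% figures then no longer apply. Nor is incremental AUC always negatively related to baseline: under the same algebra the relation is zero at r = k and positive when r > k.
- **That the preload comparisons are biased, or that the covariate would repair non-fasted days.** No bias is shown. How far a linear term would absorb a non-fasted day has not been calculated, and such days could be high-leverage points.
- **That the plan relies on test-day blood to verify fasting.** The sentence is a caveat about compliance, qualified by the next remark that not all cases can be inferred.
- **That the same correction belongs in the regressions of intake on AUC.** Those models, with "AUC of endocrine metabolic marker and energy expenditure (calculated from height and weight) as covariates", ask which marker explains most variance in intake. Adding the fasting value changes that question.

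The primary outcome is energy eaten at the ad libitum meal, and section 5 describes the preload mainly as a way to create variation in intake. This limits the weight of the point.

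**Conclusion.** The point holds as a matter of precision in an analysis that does not concern the primary outcome. The written model has no same-day fasting term, and the undefined AUC means a reader cannot tell whether baseline variation is left in the residual or removed with a fixed coefficient. Neither option has lower residual variance than covariate adjustment.

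The size is uncertain. For total AUC it runs from no gain at r = 0 to 49% less residual variance at r = 0.7, and the documents do not say where in that range any marker lies. For incremental AUC the gain is (k − r)² and can also be zero. The conclusion assumes a pre-preload test-day sample assayed for the same markers, a pooled within-subject error, and simple baseline subtraction where AUC is incremental.

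**What to change.** 1. State whether AUC is total or incremental, and which sample is its baseline.
2. In the nutrient-sensing model, add the marker's same-day pre-preload value as a covariate, split into the person's mean over the four days and that day's deviation from it. The split keeps between-person and within-person slopes apart. Keep the preload factors and the subject effect as stated.
3. Leave the regressions of intake on AUC unchanged, or add a baseline-adjusted version only as a sensitivity analysis.

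With the covariate in place, total AUC and simple baseline-subtracted AUC give the same preload contrasts, so the choice between them no longer affects this analysis. The cost is a short addition to the plan and about one of 66 within-subject degrees of freedom. No new data are needed if the first test-day sample is assayed for the same markers, and the sponsor should confirm that. Section 3 says data collection had not finished, so the term could still be prespecified at that point.
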